### 3.3. Study Assessments

## 3.3.1. Demography and Medical History

Recording of demographic data will be done at the screening visit (Visit 1) and include date of birth, race and gender. Medical History will be recorded as judged relevant by the Investigator.

## 3.3.2. Physical Examination

Physical examinations will be performed at screening (Visit 1) and at the End-of-Study visit. The complete physical examination will include an assessment of the following:

- General appearance
- Examination of abdominal skin (including area around stoma) and skin on upper extremities
- Neurological (reflexes and sensory screening for vibration and pin prick in extremities)
- Body Mass Index (BMI), measure and record height (cm) and weight (kg) (only at screening)

Physical examination data to be recorded on the eCRF will include:

- Normal/abnormal
- Description of any abnormalities

### 3.3.3. 12-lead electrocardiogram (ECG)

A standard resting 12-lead ECG will be obtained at screening (Visit 1). ECG will be recorded after the subject has been lying down for 10 minutes. From the ECG, normal/abnormal/abnormal specification and clinical significance of the abnormality will be recorded.

#### 3.3.4. Vital signs

Vital signs will be measured at screening (Visit 1), at day -1 and 1 during each treatment visit, and at the End-of-Study visit. Vital signs consist of sitting pulse and sitting blood pressure, and will be measured after the subject has been seated for at least 5 minutes.

Pulse and blood pressure will be determined while the subject is seated using a generally accepted method.

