#### Figure 1 Study design

#### 3.2. Study visits

Table 1 lists all of the assessments and indicates with an "X" the visits when they are performed. Table 2 lists the assessments during the treatment visits in more detail. All the obtained data must be supported in the subject's medical records (or equivalent), i.e. source documentation.

	Study code:	IPO-001
Clinical Study Protocol	Version No:	5.1
	Date:	26 MARCH 2019

Subjects who for any reason discontinue study drug before completing the study should be scheduled for an End-of-Study visit as soon as possible, at which time all of the assessments listed for the End-of-Study visit will be performed.

Procedure	Scree- ning		eatme Visit 1		Return to Duodopa 1		eatme Visit 2		Return to Duodopa 2			Treatment Visit 3		Infudopa s.c. Follow- Up Visit	End-of-Study Visit
Day within study period	-60 to -2	-1	1	2	3 days minimum	-1	1	2	3 days minimum	-1	1	2	3-5	30 days after Infudopa s.c. Day 2 (+/- 5 days)	30 days after V4, Day 2  (+/- 5 days)
Visit	1			2				3				4		F-U 	5
In house confine- ment		х	х	х		х	x	x		х	x	х			
Informed consent	х														
Demography & Medical History	х														
Physical examination	х														х
12-lead ECG	х														
Vital signs	х	х	х			х	х			х	х				х
Height, weight	х														
Previous / concomitant treatment	х	х				х				х					Х
Use of per protocol drugs during levodopa nighttime withdrawal		Х	Х	X		X	X	X		Х	x	Х			
Pregnancy test (for females)	х	x				x				х					
Laboratory	X9		х	х			х	х			х	х			х

Study code:	IPO-001
Version No:	5.1
Date:	26 MARCH
	2019

In-/exclusion criteria	x	x				X1				X1					
Randomi- zation		x													
Treatments			х				х				х				
Inspection of local dermal area/scoring		x	х	х		х	х	х		х	х	х		х	Х
Photo of local dermal area		X 		x		X4		х		X4		х		X 	X 
Blood PK samples⁵			х	х			х	х			х	х			
Adverse Events	X6	х	х	х	X7	х	х	х	X7	х	х	х	X7	х	х
Study completion form															х
Efficacy measure- ments (video, PKG)			х	X 			х	X 			x	X 			

 At the discretion of the Investigator, the subjects could continue the study if any deviation to the inclusion/exclusion criteria is not clinically relevant and should not alter study integrity.

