### Table 2. Assessment schedule, Treatment Visits

Day within visit	-1											1													2		
Time point (h)	after noon	Pre dose	0	15 min	30 min	1	1,5	2	2,5	3	3,5	4	5	6	7	8	9	10	12	14	16	16,5	17	17,5	18	23	24
Vital Signs	х	х																									
Pregnancy Test (for females)	х																										
Randomization 	x																										
In-/exclusion criteria 	x																										 
Previous / concomitant treatment	x																										
Use of per protocol drugs for levodopa abstinence	х	х																			х	х	х	х	х	х	х
Treatment			х	х	х	х	х	х	х	х	х	х	х	х	х	х	х	х	х	х	х						
Inspection of local dermal area/scoring	х							х								х					х						х
Photo of local dermal area	х																										х
Food 							х					х				х			х								х
Adverse Events 	х	х	х	х	х	х	х	х	х	х	х	х	х	х	х	х	х	х	х	х	х	х	х	х	х	х	X5
Video recording 		х					х						х	х	х					X6							
PKG		х	х	х	х	х	х	х	х	х	х	х	х	х	х	х	х	х	х	х	х	х	х	х	х	х	х
Blood PK samples 			х	х	х	х	х	х	х	х	х	x	х	х	х	х		х	х	х	х	х	х	x	х	x	х
Laboratory Tests 																											X 

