**Clinical Study Protocol** 

Study code:	IPO-001
Version No:	5.1
Date:	26 MARCH 2019
	2013

|--|

Randomization, only at Treatment Visit 1

At the discretion of the Investigator, at treatment visit 2 and 3, the subjects could continue the study if any deviation to the inclusion/exclusion criteria is not clinically relevant and should not alter study integrity.

Adverse Events collected throughout the study as described in section 7.

Including question at day 2 about subject's experience during the treatment day.

Starting 15 (±5) min after the blood PK sampling. Assessment at 14 h can be omitted for practical reasons (exact reason documented in the eCRF).

Laboratory tests on Day 2 only at the third Treatment Visit (according to Table 1).

Low-protein snack is allowed between meals if needed

PK sampling should be prioritised at time points when more than one procedure is scheduled at the same time point

This time point samples only for total and ionized calcium and magnesium in serum, and blood base excess.

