#### 5.1.2. Dose adjustments during treatment and temporary interruptions of infusion

No extra LCIG infusion doses will be allowed (extra bolus doses are not possible to provide with the Infudopa pump system).

A movement disorder specialist will be present during the first 4 hours of treatment to clinically evaluate the efficacy of the given treatment and to adjust doses to avoid problematic under- or overtreatment. After the first 4 h the movement disorder specialist is available as needed for the

rest of the infusion period. If the subject experiences mild and easily endurable Off-symptoms or symptoms of overtreatment the infusion rate will not be changed. Non-levodopa containing medication such as benzodiazepines or paracetamol can be used as determined appropriate by the investigator. If a subject treated with Infudopa after the first hour of treatment is uncomfortably "OFF" by comparison to what he/she experiences with the regular treatment with Duodopa, the investigator can increase the infusion rate of Infudopa by 10-20%. Such increases may be repeated once in the following 2 h and on maximum two further occasions during the following treatment period. If the subject develops severe symptoms of overtreatment, such as uncomfortable dyskinesia, disturbing nausea, symptomatic hypotension or hallucinations, the infusion will be stopped for 10 minutes, reduced to minimum flow 1.4 mL/h for 20 minutes and then resumed at an infusion rate 20% lower than the preceding. The decision to stop infusion can be taken by the investigator or a study nurse who must immediately contact the investigator for further advice. A temporary stop of infusion may be repeated every second hour until symptoms are manageable or uncomfortable hypokinesia develops. All changes in infusion rates will be recorded.

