## 8.2. Statistical analysis

Statistical assessments of dosage normalized levodopa AUC0-inf, AUC0-last, AUC0-16, AUC0-2, AUC2-16, and AUC8-16 by analysis of variance (ANOVA) will be made on the logarithmic values, with back-transformation to nominal values of point estimates and confidence interval (CI). These variables will also be tested with dosage un-normalized values. The terms to be used in the ANOVA model will be sequence, patient within sequence, period, and formulation (i.v. or s.c. Infudopa and Duodopa; test and reference, respectively).

The statistical method for testing relative dosage normalized levodopa bioavailability will be based on the 90% CI for the ratio of the population means (test/reference). These statistical tests will also be done with dosage un-normalized values. The acceptance range for AUC ratio of the 90% CI for levodopa will be 0.80 to 1.25. These tests will be performed for Treatment 1 (i.v.) and Treatment 2 (s.c.) vs. Treatment 3 (Duodopa; reference) comparison, and for Treatment 1 (i.v. reference) vs. Treatment 2 (s.c.).

For each individual will be calculated the COV (coefficient of variation or % standard deviation; SD) for plasma concentration between 2 and 16 h by dividing the SD for each individual curve with the mean value of plasma concentration between 2 and 16 h. The mean value of plasma concentration will be calculated for each curve as AUC2-16/14. Basic statistics for the COV will then be calculated per treatment group. The one-sided 90% CI of the intersubject COV will be calculated for Treatment 1 (i.v.) and Treatment 2 (s.c.) vs. Treatment 3 (Duodopa; reference) comparison, and for Treatment 1 (i.v. reference) vs. Treatment 2 (s.c.). It will also be tested with paired t-tests if there are significant differences in intersubject COV between treatments (i.v. vs. Duodopa, s.c. vs. i.v., and s.c. vs. Duodopa).

The level of significance will be p=0.05.

Safety will be summarized with the standard set of AE summary tables, and descriptive summary statistics of vital signs by visit and change from baseline.

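### Every treatment-visit vital sign is scheduled before that visit's dosing, so the planned vital-sign summary cannot show an effect of the infusions; separately, Table 1 and a Table 2 footnote conflict on Day 2 laboratory tests.

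*Protocol*

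**What the plan says.** **Vital signs.** Protocol section 3.3.4 gives days but no clock times: "Vital signs will be measured at screening (Visit 1), at day -1 and 1 during each treatment visit, and at the End-of-Study visit". Section 3.2 leaves the detail to the second schedule table: "Table 2 lists the assessments during the treatment visits in more detail". In that table ("Table 2. Assessment schedule, Treatment Visits") the vital-signs row has two marks, the Day -1 afternoon and Day 1 pre-dose. Table 1 has no vital-signs mark on Day 2. Section 6.2 lists vital signs among the variables that evaluate the safety of the study medication, and section 8.2 plans "descriptive summary statistics of vital signs by visit and change from baseline". Section 5.1.2 gives as examples of severe overtreatment "uncomfortable dyskinesia, disturbing nausea, symptomatic hypotension or hallucinations".

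**Laboratory tests.** Table 1 marks laboratory tests at screening, on Day 1 and Day 2 of each of the three treatment visits, and at End-of-Study. Footnote 7 to Table 2 reads "Laboratory tests on Day 2 only at the third Treatment Visit (according to Table 1"). Footnote 10 to the same table adds: "This time point samples only for total and ionized calcium and magnesium in serum, and blood base excess". The text at hand shows no marker for footnote 10 in the body of the table.

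**The concern.** Safety is the first secondary objective in section 2.2, and vital signs are one of its named variables. A summary of change in vital signs informs about the treatments only if some value is taken while a treatment is acting. If every reading at a treatment visit precedes the dose, i.v. Infudopa, s.c. Infudopa and Duodopa will look alike in that table whatever they do to blood pressure or pulse. A reader could then take the absence of a difference as reassurance. This is a gap in what is collected, so an analysis plan cannot close it.

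The laboratory conflict is a different matter. Sites cannot follow both Table 1 and footnote 7. The choice decides whether each patient has a Day 2 panel after each treatment or only after whichever treatment came last. Section 1.4 says safety laboratory tests were included to watch for effects of citrate and phosphate, and the s.c. buffer has been changed since the first five patients.

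**Working it through.** The plan states no figure to reproduce here; the check is a count of schedule marks, followed by a precision calculation for the laboratory tests.

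**1. Vital signs: readings by time**

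| Source | Per treatment visit |
|---|---|
| Section 3.3.4 and Table 1 | one on Day -1, one on Day 1, none on Day 2 |
| Table 2, 27 time columns | Day -1 afternoon; Day 1 pre-dose; no mark from 0 h to 24 h |

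The sources agree on two readings per visit, which argues against a mark lost in text extraction. Over three visits this is 3 × 2 = 6 readings. The number at or after the start of that visit's infusion is 3 × 0 = 0.

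**2. What each possible change would measure**

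- *Day -1 afternoon to Day 1 pre-dose.* Section 3.2 stops levodopa at least 7 h before the infusion (last dose about 23:00). This change spans the overnight abstinence and contains no study infusion.
- *Visit to visit.* The four readings at the second and third treatment visits do follow an earlier study infusion, but after at least three days back on Duodopa. With the 60 to 90 minute half-life given in section 1.1, 72 h is at least 72 / 1.5 = 48 half-lives.
- *To End-of-Study.* This reading comes about 30 days after the third treatment visit.

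None of these describes the 16 h infusion.

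**3. Laboratory: number of Day 2 panels**

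Table 1 gives 3 Day 2 panels per patient, one after each treatment. Footnote 7 gives 1, after the treatment received third. With 18 second-part patients (section 3.1) and equal numbers receiving each treatment third, 18 / 3 = 6 patients per treatment have a panel, against 18.

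**4. Laboratory: precision of a treatment difference**

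Let SD be the between-patient standard deviation of a laboratory value and ρ the correlation between two visits in the same patient. The protocol does not give ρ, so 0 to 0.9 is an assumed range. The detectable difference (80% power, two-sided 0.05, normal approximation) is (1.96 + 0.84) × SE = 2.8 × SE.

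- Footnote 7, between patients: SE = SD × √(2/6) = 0.58 SD
- Table 1, within patients: SE = SD × √(2(1 − ρ)/18)

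| Schedule | ρ | SE (SD units) | Detectable difference (SD units) |
|---|---|---|---|
| Footnote 7 | not used | 0.58 | 1.62 |
| Table 1 | 0 | 0.33 | 0.93 |
| Table 1 | 0.5 | 0.24 | 0.66 |
| Table 1 | 0.9 | 0.11 | 0.30 |

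With 6 per group the normal approximation slightly flatters the footnote 7 row.

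**The case against.** The strongest reply is that safety here rests mainly on other data. Section 2.2 puts the focus on local tolerability, which Table 2 inspects at 2, 8, 16 and 24 h of every treatment visit. Adverse events are recorded throughout. A movement disorder specialist is present for the first 4 h and available afterwards, and symptomatic hypotension would be acted on and recorded. The active substances are known and the patients already receive them. All of this stands, and it limits the point to one descriptive summary. It does not rescue that summary: readings prompted by symptoms do not give a comparable value for each treatment.

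Some stronger readings are tempting, and the protocol does not support them:

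- *That the safety summaries as a whole cannot show a treatment effect.* Adverse-event and local-tolerability data exist during and after infusion at every visit.
- *That laboratory values under footnote 7 are confounded with period.* They would all come from period 3, so period is the same for every treatment, and order is randomized. What is lost is the within-patient comparison and precision.
- *That the next vital sign after any treatment is about 30 days away.* This holds only after the third treatment visit; otherwise it is Day -1 of the next one.
- *That a planned laboratory comparison fails.* Section 8.2 names none, and tabulation may sit in a separate analysis plan.
- *That no other laboratory data exist.* Table 1 marks Day 1 tests, and footnote 10 shows a further restricted sample that cannot be placed from the text at hand. The laboratory row of Table 2 may have lost marks in extraction.

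**Conclusion.** The point holds for vital signs. All 6 treatment-visit readings per patient precede that visit's dosing, so the summary planned in section 8.2 contains no value during or shortly after any infusion and cannot show an effect of the treatments. This rests on Table 2 as read, which agrees with Table 1 and section 3.3.4.

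Footnote 7 and Table 1 contradict each other on Day 2 laboratory tests, 1 visit against 3, and the footnote cites the table that it contradicts. If the footnote governs, about 6 of 18 second-part patients per treatment have a Day 2 panel, assuming balanced sequences. That leaves a randomized between-patient comparison within period 3, with a standard error of 0.58 SD against 0.33 to 0.11 SD under Table 1 for ρ from 0 to 0.9. The comparison would be weak, not impossible. Both parts should be corrected; neither touches the primary pharmacokinetic analysis.

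**What to change.** 1. **Vital signs.** At each treatment visit, add sitting pulse and blood pressure at one time when staff already inspect the skin (2, 8 or 16 h), the same time at all three visits, and mark it in Table 2 and section 3.3.4. The 2 h point falls half an hour after breakfast and the 8 h point coincides with dinner, so fix the order relative to the meal; at 16 h, take the reading before the pump stops. Blood sampling keeps the priority that Table 2 gives it.
2. **Definition.** In section 8.2 define change as that reading minus the same-day pre-dose reading, summarised by treatment. The change will include the return of levodopa after the night, so the informative contrast is between treatments.
3. **Laboratory.** Reconcile footnote 7 with Table 1 and place the footnote 10 sample, preferably so that samples are taken at the same post-dose time after each treatment.

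The cost is one extra cuff reading per visit (3 per patient, 3 × 18 = 54 in the second part) and a correction of the schedule tables. If Table 1 is the intended laboratory schedule, item 3 adds no sample to it; if footnote 7 is, it adds two Day 2 panels per patient, to be checked against the 450 mL blood limit in section 6.3.2.

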### 3.3.5. Previous and concomitant treatment

Previous medication will be recorded as part of the medical history during the screening visit, as judged relevant by the Investigator. Concomitant medication during the study will be asked about and recorded in the eCRF at screening (Visit 1), and at day -1 during each treatment visit, and at the End-of-Study visit.

### 3.3.6. Use of permitted drugs during night time levodopa abstinence

Concomitant treatment with dopamine agonists as per the subject's regular medication schedule is allowed throughout treatment visits. The patient is however not allowed to use any levodopacontaining drug other than the IMPs between 23:00 on Day-1 and the reinstatement of Duodopatreatment in the morning of Day 2 of treatment visits. During this time levodopa-abstinence symptoms like Restless Leg Syndrome (RLS), and Parkinson OFF-symptoms can be treated with paracetamol, oxazepam and short acting dopamine agonists like pramipexol, ropinirol or temporarily worn rotigotine patches. Temporary use of the following drugs during night time levodopa abstinence must be noted in the eCRF (dose and time of administration): paracetamol, oxazepam, pramipexol, ropinirol, rotigotine, but should not be noted as change of concomitant medication.

#### 3.3.7. Inspection of local dermal area/scoring including photos

Inspection of local dermal area, including adverse event scoring, and photos will be performed at the site in Gothenburg at day -1 and day 2 during the treatment visits. The same assessments will be made at the Infudopa s.c. follow-up visit and the End-of-Study visit by the local Investigator. In addition to visual inspection and photo documentation of the skin area the area will be assessed for increased subcutaneous consistency, tenderness and pruritus (itching). Pain, tenderness and itching, respectively, will be rated by the subject using a horizontal 10 cm visual analogue scale (VAS) (Furue et al, 2013 and Younger et al, 2009). In the event of any occurrence of noduli or increased subcutaneous consistency, it will be photographed, and then the approximate borders will be delineated on the skin with a pen and photographed.

Photos will always be taken at day -1 and day 2 of each treatment visit according to provided instructions, and to document any abnormalities at the Infudopa s.c. follow-up visit, and at the End-of-Study visit. Photos of the skin area will be taken using a dark background behind the subject.

Perpendicular artificial lighting will be used and the subject will be asked to relax muscles. The subject will be photographed in dorsal recumbent position on all occasions. A 10 cm paper ruler tag will be placed at on the skin at the side of the infusion site and the full length of the ruler included in view. The subjects face or other identifiable features will not be included.

The photos will be assessed and scored according to the Draize Score (refer to Appendix B) by two blinded and independent dermatologists, and photos will be randomized between time, subjects and treatments for the assessment. The assessors will be trained before the study, and the order of the photos will be broken when all assessments are finalized. Estimation of area of the affected skin will be made, using the above-mentioned ruler as a calibration unit.

Adverse events involving the skin will be evaluated by study personnel when prompted by the subject and at the pre-defined time points. At the pre-defined time points any occurrence of the following pre-defined symptoms will be assessed and severity rated: erythema, discoloration, pain, pruritus, subcutaneous nodulus or tenderness. Predefined infusion related **adverse events** involving the infusion sites are: Acute transient infusion site reaction, Continuous infusion site reaction and delayed infusion site reaction which when appropriate can be described with other terms listed under the class "General disorders and administration site conditions" - "Infusion site reactions" or "General disorders and administration site conditions" - "Implant and catheter site reactions" See:

http://bioportal.bioontology.org/ontologies/MEDDRA/?p=classes&conceptid=http%3A%2F%2Fpurl. bioontology.org%2Fontology%2FMEDDRA%2F10018065. When appropriate, free text terms can be used.

## 3.3.8. Laboratory Assessments

Blood and urine samples will be taken at the times indicated in the assessment tables (Table 1 and 2). The following samples will be collected and variables measured (see 6.3.2 for total volume):

- Clinical chemistry (calcium, phosphate, total bilirubin, alkaline phosphatase, urea, urate, chloride, creatinine, total protein, albumin, aspartate transaminase (AST), alanine transaminase (ALT), sodium, potassium, creatine kinase (CK), homocysteine, prothrombin complex (PTK-INR), activated partial thromoplasmin time (APTT))
- HIV and hepatit B and C
- Haematology (haemoglobin, platelet count, haematocrit, red blood cell (RBC) count, white blood cell (WBC) count with differentials)
- Total and ionized calcium and magnesium in serum, and blood base excess
- Urinalysis (pH, ketones, glucose, proteins, blood), urine pregnancy test, 10 mL midstream.
- Blood PK samples; Levodopa (LD), carbidopa (CD), and 3-O-methyldopa (3-OMD)

Blood and urine samples (except for PK samples) will be analysed at the site or at the local hospital laboratory according to routine procedures, and then destroyed.

	Study code:	IPO-001
Clinical Study Protocol	Version No:	5.1
	Date:	26 MARCH 2019

Laboratory values outside the reference limits suspected to be of any clinical significance will be re-checked, but without further recording in the eCRF. Subjects in whom the suspected clinical significance is confirmed at the repeated sampling will either not be included or, if already included, will be followed until normalization or for as long as the Investigator considers necessary.

The PK blood samples will be stored at  $-20^{\circ}$ C until shipment to laboratory for analysis.

Details for biological sample handling will be specified in a study specific Laboratory Manual.

Levodopa, carbidopa, and 3-OMD will be analysed at a certified laboratory with Good Laboratory Practice (GLP) standard, and the bioanalytical method should be fully validated according to European Medicines Agency (EMA) Guideline on bioanalytical method validation (July 2011, EMAE/CHMP/EWP/192217/2009). The lower limit of quantification (LLOQ) will be at least 15 ng/mL for plasma of both active ingredients levodopa and carbidopa. Separate bioanalytical study plan will be prepared and approved before study sample analysis.

